4. Design and Procedures: This will be an unblinded, open-label study enrolling newly diagnosed patients with IPF. We plan to consent 50 subjects including screen fails with a goal of obtaining 30 newly diagnosed individuals with IPF prior to initiation of IPF therapies. 20 subjects will be monitored after the initiation of therapy, 10 subjects will be enrolled that do not start antifibrotic therapy. No subject will be excluded from the study on the basis of gender or ethnicity. IPF is an aging disease with highest incidence in subjects >50 years of age, and therefore subjects will be expected to be >50 years of age. Subjects will be obtained from providers in the Duke Pulmonary Clinics. Informed consent will be

Using Xenon MRI to Evaluate the Efficacy of Therapies for Idiopathic Pulmonary Fibrosis

obtained before a subject begins any study intervention. Subjects will undergo an approximately hour long comprehensive MRI protocol, including administration of multiple doses of HP ^{129}Xe . The subjects will have this initial study prior to initiation of IPF therapies. Then the subjects will have repeat studies at 3, 6 and 12 months following the initiation of therapy. Additional studies including pulmonary function studies, serum for biomarkers, 6 minute walk distance (only at screening visit, 3 month and 6 month visit) and a HRCT (only at the screening visit and 6 month visit) will be performed to determine how ^{129}Xe MRI performs relative to standard of care evaluations for IPF. Finally, following the study visits the research team will prospectively follow the patients' clinical course through periodic reviews of the medical record.

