Prior to consideration for the study, all patients will have their IPF diagnosis formally confirmed at the Duke multidisciplinary ILD conference. Either through discussions at the multidisciplinary conference or through referral from the patient's pulmonologist, the study coordinator will identify potential patients. With their primary doctors approval, the coordinator will have an initial screening phone call with the patient to assess their interest in the study (V0). If the patient is interested, a screening visit will occur (V1). The screening visit will start with a history and physical exam and a review of the protocol to obtain informed consent. Following informed consent, the patient will undergo spirometry including lung volume and a DLCO measurement, assessment of a 6 minute walk distance (6MWD) and a HRCT scan if not done at the initial visit with the pulmonary provider. Venous blood will be obtained to get cells for DNA and RNA and plasma for biomarkers, a nasal swab will be performed, and a urine sample will be obtained from the subject.

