Using Xenon MRI to Evaluate the Efficacy of Therapies for Idiopathic Pulmonary Fibrosis

be performed at the other pre-specified visits. At these 3, 6 and 12 month visits, as a part of the study, subjects will undergo repeat ^{129}Xe MRI studies and a venous blood draw to obtain cells for RNA and serum for biomarkers, a nasal swab, and urine sample collection. Following the 12 month visit, a chart review will be performed at 6 month intervals and clinical IPF characteristics will be recorded to determine clinical outcomes, for a period of 5 years (V6). No additional direct study contact with the patients will occur after the 12 month visit (V5). For subjects lost to follow-up prior to completing all 4 in person visits, we will request written permission in the informed consent to use their standard of care (SOC) assessments to obtain clinical data such as physical exam, vitals, PFTs and 6MWD that pertain to the timepoints noted above (3 months, 6 months and 12 months post initiation of therapy).

5. Selection of Subjects: The population to be studied will consist of patients with a physician diagnosis of idiopathic pulmonary fibrosis.

Inclusion/Exclusion Criteria

Inclusion Criteria

Subjects must meet all of the following inclusion criteria to be eligible for enrollment into the trial

1. Outpatients of either gender, age > 18.
2. Willing and able to give informed consent and adhere to visit/protocol schedules. (Consent must be given before any study procedures are performed)
3. Clinical diagnosis of IPF by confirmed by multidisciplinary diagnosis and naïve to treatment with an approved IPF therapy (either nintedanib or pirfenidone)

Exclusion Criteria

Subjects presenting with any of the following will not be included in the trial:

1. Subject is less than 18 years old
2. Subjects who have been previously on either pirfenidone or nintedanib
3. MRI is contraindicated based on responses to MRI screening questionnaire
4. Subject is pregnant or lactating
5. Resting oxygen saturation on room air <90% on supplemental oxygen
6. Respiratory illness of a bacterial or viral etiology within 30 days of MRI
7. Subject with ventricular cardiac arrhythmia in the past 30 days.
8. Subject has history of cardiac arrest within the last year
9. Subject does not fit into ^{129}Xe vest coil used for MRI
10. Subject deemed unlikely to be able to comply with instructions during imaging

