Although sensitivity to therapy response is expected to be highest for the imaging metrics, the study has been conservatively powered on the basis of the spectroscopic RBC:barrier ratio, which thus far, is most well-documented of the ¹²⁹Xe metrics in the literature. Early studies, which did not control carefully for lung inflation reported a variability of 6.6% in this metric. Moreover, a recent study of natural progression in a group of IPF patients (n=18, on a mix of treatments or untreated) revealed a decline in RBC:barrier of 20% in this metric over the course of 6 months. We assume that we will observe a smaller decline in RBC:barrier in our cohort, which will all receive treatment, and estimate that only a 10% decline will be observed at 12 months. Given this estimate of variability and effect size, and requiring 90% power, would be achieved with a sample of only 5 patients. Based on established patterns in our clinics, we expect roughly half the patients to receive pirfenidone with the other half receiving nintedanib. Assuming that one of the drugs reduces RBC:barrier decline to only 5% over 12 months, whereas the other yields a decline of 10%, would require a sample of 19 patients, which is just achievable with the sample of 20 patients expected to be enrolled.

Baseline Repeatability and Prespecified Futility Analysis – As this is a new clinical study with unknown efficacy in detection a preliminary analysis of the data will be performed. Following completion of the first 10 patients in the study the study team will perform an analysis for futility based on test – retest variability. Baseline repeatability of each of the ¹²⁹Xe metrics will be assessed using Bland- Altman plots, and a pairwise, two-tailed *t*-test will be used to check for significant differences. For each derived parameter, the coefficient of variation will be calculated. Our threshold to stop the study is if the RBC:Barrier ratio is outside of 95% CI on test-retest of $\pm 20\%$ of the dynamic range. We estimate the 95% confidence interval to be better than $\pm 10\%$ with this sample size.

Correlation between ¹²⁹Xe metrics, CT scores, and clinical tests will be evaluated using the Pearson correlation coefficient.

To measure changes from baseline, we will calculate the mean, standard deviation, median and range of each metric, and at each time point, the 95% confidence interval for means and averaged changes relative to baseline will be provided. Changes compared to

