13. Data and Safety Monitoring: Subjects will be monitored before, during and after each dose of xenon to assess for adverse events and changes in vital signs. The parameters monitored include the following: subject assessment of anesthetic/analgesic effects, heart rate, and SPO_2 . The subjective sense of analgesia is assessed by inquiring about how the subject feels after administration of the xenon dose. The subject will be asked to describe how they feel as well as about specific symptoms including: dizziness, light-headedness, numbness, euphoria, sleepiness, and tingling in extremities. Heart rate will be measured before and after each xenon dose. Changes in heart rate of greater than $+/ - 20\%$ are considered significant. If the subject is to receive another dose, the next dose will not be administered until the heart rate is within 20 % of its baseline value. If the subject has received their last dose, they will be observed until their heart rate is within $+/ - 20\%$ of its base line value or until the end of the observation period, whichever is longer. SPO_2 is measured at baseline and after each xenon dose. A decrease of SPO_2 by greater than 5% is considered significant. If the subject is to receive another dose, the next dose will not be administered until the SPO_2 is within 5 % of its baseline value. If the subject has received their last dose, they will be observed until the SPO_2 is within 5% of its baseline value or until the end of the observation period, whichever is longer. The subject will be monitored for the duration of the xenon dose and post procedural period as well as the MRI with contrast by a qualified medical professional.

Research Specimens: Research material, which will be collected from human subjects and includes; serum, and DNA. These data will be collected for research purposes, but remain available, if need and agreed to, by the subject for future research use. DNA will be stored indefinitely. Samples will be de-identified by assigning a code only accessible to PIs and study team, DNA will primarily be used for this study but could also be used for future studies (outlined in the consent using standardized language). If sample is provided to outside investigators, the DNA and clinical information will only be identified by the assigned code.

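### The protocol disagrees with itself on the baseline biomarker specimen: plasma in the V1 procedures, serum at 3, 6 and 12 months and wherever no visit is named

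*Combined protocol and SAP*

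**What the plan says.** Four places in the protocol describe the blood specimen.

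- **Section 4, V1 procedures:** the blood draw is to yield cells for DNA and RNA, and "plasma for biomarkers, a nasal swab will be performed".
- **Section 4, follow-up procedures:** "At these 3, 6 and 12 month visits, as a part of the study", subjects have "a venous blood draw to obtain cells for RNA and serum for biomarkers".
- **Section 4, design summary (first paragraph):** "Additional studies including pulmonary function studies, serum for biomarkers, 6 minute walk distance". The same sentence restricts the walk test and the HRCT to named visits but puts no such limit on the serum.
- **Section 13, Research Specimens:** "Research material, which will be collected from human subjects and includes; serum, and DNA". Plasma is not listed.

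The Schedule of Events and its footnotes have no row for blood or biomarker sampling. Nowhere does the protocol say that both specimen types are drawn at any visit, or that a change of type after V1 is intended.

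On analysis, Section 12 says: "To measure changes from baseline, we will calculate the mean, standard deviation, median and range of each metric". The metrics it names are xenon imaging and spectroscopic measures and a CT fibrosis score. It also refers to clinical tests. It names no blood biomarker, assay or biomarker endpoint.

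**The concern.** Plasma and serum are different specimens, and an assay may read differently in each. A coordinator working from the two sets of visit instructions would bank plasma before treatment and serum at every visit afterwards. Specimen type would then coincide exactly with the split between baseline and follow-up, and a within-subject change could not be told apart from a specimen effect.

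The loss would be permanent. V1 is the pre-treatment visit in patients who have never taken pirfenidone or nintedanib, so the sample cannot be retaken once therapy has begun. The protocol repeats the biomarker draw at each in-person follow-up visit and lists biomarkers among the additional studies done alongside MRI. Much of the value of repeated sampling lies in having a comparable baseline.

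**Working it through.** No figure in the plan can be reproduced here, and the point depends on no alpha, power, SD or effect size. The check is a comparison of texts, a short identifiability argument and a count.

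**1. Specimen by visit**

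| Source | V1 | V3, V4, V5 |
|---|---|---|
| Section 4, visit procedures | Plasma | Serum |
| Section 4, design summary | Serum (no visit limit) | Serum (no visit limit) |
| Section 13, Research Specimens | Serum (no visit named) | Serum (no visit named) |
| Schedule of Events | No row | No row |

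The sources that mention blood agree on follow-up and disagree only about V1. The one that says plasma is the operative instruction for that visit.

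**2. Consequence if the visit procedures are followed literally**

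For subject i at follow-up visit t, let d(i,t) be the true biomarker change since V1 and s(i,t) the difference between a serum and a plasma reading of the same blood. The observed change is

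serum value at t − plasma value at V1 = d(i,t) + s(i,t).

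With plasma only at V1 and serum only afterwards, an indicator for specimen type is identical to an indicator for follow-up versus baseline. The data identify the mean of d + s but not d alone. No adjustment within these data separates the two, because no subject has both specimen types at one visit. The size and direction of s depend on the assay and are not in the documents, so no numerical bias can be given.

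**3. What is and is not affected**

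- Change from V1 to 3, 6 or 12 months in a blood biomarker: affected.
- Change between follow-up visits, such as 3 to 12 months: not affected, since all are serum.
- Correlation of a biomarker with MRI within one visit: not confounded, since all subjects at that visit share a specimen type.
- RBC:barrier sample size and the test-retest futility rule: not affected, since neither uses blood.

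**4. Number of baseline-to-follow-up pairs**

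Section 4 plans 20 subjects monitored after starting therapy and 10 who do not start antifibrotic therapy. It times the 3, 6 and 12 month visits from the start of therapy.

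- Treated subjects: 20 x 3 = 60 pairs.
- If the untreated subjects are sampled on the same schedule: (20 + 10) x 3 = 90 pairs.

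Both counts assume that every subject completes every visit. The second also needs a visit schedule for untreated subjects that the protocol does not state.

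**The case against.** The best reply is that plasma in the V1 paragraph is a drafting slip. The design summary says serum with no visit limit, in a sentence that does limit other procedures to named visits, and the specimens paragraph says serum too. The specimen wording is loose in general: Section 13 omits the RNA, nasal swabs and urine that Section 4 collects. This stands. A reader might infer that the protocol plans a switch from plasma to serum, so that no patient will have a matched baseline. The documents do not support that; they support only a contradiction about V1. The slip explanation does not remove the problem, however. The V1 paragraph is what staff would follow at V1, and an incomplete list in Section 13 is a weak basis for overriding it.

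The second reply is that no planned analysis is damaged. Section 12 names no blood biomarker, and its change-from-baseline analysis concerns metrics among which biomarkers are not listed. This also stands. The affected analysis is inferred from the repeated sampling and is exploratory. A reader might go further and infer that the comparison of biomarkers with MRI is compromised in general. That does not follow, because the comparison is sound within any single visit.

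A third reply is that a laboratory manual may fix the tube type. The protocol cites none for blood handling, and any such manual would still conflict with one of these statements.

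**Conclusion.** The contradiction is real and should be resolved, but its reach is limited. The documents disagree on the V1 biomarker specimen. Only if the visit-level instructions are followed literally does change from V1 become confounded with specimen type, and then it does so for every such pair: 60 on the schedule that the text states for treated subjects. The figure of 90 is an upper limit that rests on untreated subjects sharing that schedule. The harm falls on an exploratory measure with no specified analysis, and its numerical size cannot be derived from the documents. The primary power argument, the futility rule and all metrics named in Section 12 are untouched. The point still merits action because the correction is cheap, while a mismatched pre-treatment sample cannot be replaced.

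**What to change.** Reconcile the four statements: the design summary, the V1 procedures and the follow-up procedures in Section 4, and Research Specimens in Section 13. Each should name the same specimen type for V1, V3, V4 and V5. If both types are wanted, both should be collected at all four visits. Add a biomarker sampling row to the Schedule of Events that gives the specimen and the visits, and say there whether the untreated subjects are sampled and when.

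If samples have already been taken as the visit procedures read, do not compute change from V1 across specimen types without a bridging comparison, meaning paired plasma and serum from the same draw run on the same assay. Otherwise confine longitudinal biomarker summaries to the follow-up visits, and MRI comparisons to within-visit ones.

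The cost is a wording change. If both types are chosen, it may also mean an additional tube at a draw already planned; this is an assumption, since the protocol does not describe tubes or volumes.

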IPF manifests in a spatially heterogeneous manner pathologically defined as areas of normal lung in close approximation to areas of fibrosis. Therefore, we expect that therapeutic responses would be regional. Thus, to detect progression and therapy requires localizing effects on structure and function, and monitoring these regions over time. Advances in 3D pulmonary magnetic resonance imaging (MRI) now make this possible. Although high resolution computed tomography (HRCT) is required for IPF diagnosis, it is poorly suited to monitor therapeutic response. CT detects structural abnormalities, but the earliest harbinger of changing disease status is *function*. Additionally, CT scans and particularly HRCTs require use of ionizing radiation. The ability to image both function and structure is now ideally served by recent advancements in MRI. Because ¹²⁹Xe, like oxygen, must traverse the interstitial barrier to reach capillary blood, ¹²⁹Xe signal in RBCs is exquisitely sensitive to barrier thickness. ¹²⁹Xe in RBCs has a unique frequency shift, allowing it to reveal interstitial thickening of only a few microns. The exquisite sensitivity to increased blood-gas-barrier thickness makes ¹²⁹Xe MRI uniquely suited to study pulmonary fibrosis without ionizing radiation. This has the potential to accelerate clinical trials for IPF by literally visualizing the therapeutic response on the timescale of months versus years.

Hyperpolarized ¹²⁹Xe MRI has been shown to be safe and well tolerated in a phase I clinical trial for HP ¹²⁹Xe MRI that was completed at Duke and published in the journal Radiology in 2012. Additionally, we have now published on the use of this technology in patients with IPF, asthma, COPD, and pulmonary vascular disease. These studies have enrolled in excess of 250 patients and healthy volunteers and demonstrated that inhalation of up to four 1 liter doses of HP ¹²⁹Xe was well-tolerated, generated no notable changes in measured physiologic parameters and resulted in no SAEs or withdrawals. Thus, Duke has the technical experience and infrastructure to conduct this study.

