Following these initial screening studies, the patient will undergo a ^{129}Xe – MRI exam. The details of the ^{129}Xe MRI are as follows. The subject will be escorted to the MRI suite where they will be fitted with a ^{129}Xe transmit-receive vest coil. They will then be positioned supine on the scanner bed. They will be coached about how to inhale HP ^{129}Xe from the dose delivery bags. Then the subject and bed will be moved into the scanner and they will undergo basic ^1H localizer and anatomical scans. Once localization is complete, subjects will undergo several MRI scans after inhalation of HP ^{129}Xe . Each dose will be limited to a volume less than 25% of subject lung capacity (TLC) as is the case for all protocols currently carried out under IND 109,490. After each ^{129}Xe dose, the table will be moved out of the magnet bore and the subject queried for any symptoms. The next ^{129}Xe dose and scan will be administered when the subject and study personnel are ready. Subjects will undergo a ^{129}Xe dynamic spectroscopy and calibration, and ^{129}Xe gas exchange MRI. Any given ^{129}Xe MRI scan may be repeated, if necessary. After completing this sequence, the subject will get off the MRI table, rest for 5 minutes and then undergo the same scans to assess repeatability. There is no limit to the number of ^{129}Xe scans allowed during the session, although current ^{129}Xe production capabilities generally limit this to 5 ^{129}Xe doses. After completing the ^{129}Xe portion of the scan, the ^{129}Xe coil will be removed and patients fitted with a torso array ^1H coil. They will then undergo a free-breathing ultra-short-echo time ^1H MRI to delineate lung structure.

Following visit V1, the coordinator will ask the patient and/or contact the patient to confirm the start date of an FDA approved IPF therapies (pirfenidone and nintedanib). The decision of which type of therapy will be completely at the discretion of the patient and their primary pulmonologist but will be recorded by the coordinator. Following initiation of therapy, the subject will return for visits at 3 (V3), 6 (V4) and 12 (V5) months following initiation of therapy. At that time, the subjects will undergo a physical exam, spirometry and a 6MWD (only at screening visit, 3 month and 6 month visit) if not performed as a part of their usual care. At 6 months, the subjects will also undergo a HRCT scan. This will not

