7. Consent Process: The study coordinator will consent prospective participants. If necessary, the participants will have no less than 24 hrs to consider their participation. The consenting will take place in the private room or laboratory setting with closed doors. Only the coordinator and prospective participant will be in the room during the consent process. We will encourage potential subjects to ask questions and to take as much time as needed to consider participation. If the subject wishes to consider the study overnight or longer, an additional appointment will be made for the subject to continue the consent process. From the time of initial contact until the participant completes the study they will have a coordinator's contact information.

8. Subject's Capacity to Give Legally Effective Consent: Subjects without capacity to give consent will not be recruited into this study.

9. Study Interventions: Hyperpolarized xenon will be administered in multiple doses in volumes up to 25% of subject TLC followed by a breath hold of up to 15 seconds. Subsequent ¹²⁹Xe doses will only be administered once the subject is ready to proceed. Hyperpolarized ¹²⁹Xe MRI will be used to acquire one or all of the following data:

Pre- treatment (Study V1)

1. 3-Plane Localizer
2. ¹²⁹Xe dynamic spectroscopy and calibration to test coil tuning and loading in each subject to permit optimal setting of imaging parameters.
3. ¹²⁹Xe distribution dissolved in the pulmonary interstitial spaces and capillary blood as an indicator of pulmonary gas exchange.
4. Breath-hold 3D radial MRI to delineate the thoracic cavity
5. Subjects will dismount the MRI table, rest for 5 minutes
6. 3-Plane Localizer
7. ¹²⁹Xe dynamic spectroscopy and calibration to test coil tuning and loading in each subject to permit optimal setting of imaging parameters.
8. ¹²⁹Xe distribution dissolved in the pulmonary interstitial spaces and capillary blood as an indicator of pulmonary gas exchange.
9. Breath-hold 3D radial MRI to delineate the thoracic cavity

Using Xenon MRI to Evaluate the Efficacy of Therapies for Idiopathic Pulmonary Fibrosis

Post Treatment (V3, V4, and V5)

1. 3-Plane Localizer
2. ^{129}Xe dynamic spectroscopy and calibration to test coil tuning and loading in each subject to permit optimal setting of imaging parameters.
3. ^{129}Xe distribution dissolved in the pulmonary interstitial spaces and capillary blood as an indicator of pulmonary gas exchange.

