4. Breath-hold 3D radial MRI to delineate the thoracic cavity

If any of these scans are deemed by the study team to require repeating, this may be done as needed

HRCT scans will be done in the prone position at both inspiration and expiration using the protocol commonly used in IPF clinical trials.

10. Risk/Benefit Assessment: As this is the first rigorous prospective study of its kind for using MRI to monitor patients with IPF, it is not known if the data generated will be of direct benefit to the patients participating. However, the knowledge gained from these studies is expected to benefit future patients with IPF.

Risks of Hyperpolarized ^{129}Xe Inhalation of hyperpolarized ^{129}Xe may carry some minor risks. Xenon is a general anesthetic when breathed continuously at concentrations greater than 70% for extended periods of time. In the proposed study, xenon will be delivered in a single breath, with alveolar concentrations below 25%. At these concentrations, subjects may experience transient effects including dizziness, slight tingling or numbness of the extremities, nausea, smelling of flowers, or a feeling of well-being and euphoria. These effects will wane within 1-2 minutes of exhaling the xenon and are documented in the consent forms.

Risk of HRCT: Ionizing radiation exposure for the low dose CT is estimated at 2mSievert for each scan. For both inspiratory/and expiratory scans, the total dose is estimated at 4mSievert, roughly the equivalent of 1 year of natural radiation exposure.

A second risk comes from administering HP ^{129}Xe without oxygen. This is necessary to preserve good image quality, because O_2 is paramagnetic and depolarizes the HP ^{129}Xe . Therefore, ^{129}Xe is not mixed with O_2 within the dose delivery bag, but only once it is inhaled. Administration of a single anoxic 1-liter breath has been well tolerated by subjects undergoing both ^3He MRI and ^{129}Xe MRI. After a single breath, the residual oxygen in the subject's lungs is sufficient to maintain blood O_2 saturation during the breath-hold. For each subject, their blood-oxygenation will be monitored throughout the time they are in the MRI scanner. To reduce risk, a baseline resting oxygen saturation of 90% on supplemental oxygen will be required. Furthermore, supplemental oxygen will be provided during the MRI exam as indicated.

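### The protocol sets no limit on xenon doses per session, while the multi-dose experience it cites stops at four, a number the full V1 sequence already uses

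*Combined protocol and SAP*

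**What the plan says.** **Permitted exposure.** Section 4 says "There is no limit to the number of ^{129}Xe scans allowed during the session" and adds that "production capabilities generally limit this to 5 ^{129}Xe doses". It also lets any xenon scan be repeated if necessary. Section 9 (Study Interventions) repeats that permission: "If any of these scans are deemed by the study team to require repeating, this may be done as needed". Volume is limited per dose and relative to lung size: "Hyperpolarized xenon will be administered in multiple doses in volumes up to 25% of subject TLC" in Section 9, and a similar rule (below 25% of TLC) in Section 4. Neither section gives a session total.

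**Cited safety experience.** Section 3 (Background and Significance) reports that "inhalation of up to four 1 liter doses of HP" xenon-129 was well tolerated in more than 250 patients and volunteers, with no SAEs or withdrawals. Section 10 (Risk/Benefit Assessment) describes delivery in a single breath. On the oxygen-free gas it says "Administration of a single anoxic 1-liter breath has been well tolerated by subjects".

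**Planned scans.** Section 4 says "Subjects will undergo a ^{129}Xe dynamic spectroscopy and calibration, and ^{129}Xe gas exchange MRI". At V1 the subject then rests for 5 minutes and the scans are done again. The Section 9 list for V1 has four xenon items (2, 3, 7 and 8). The list for V3 to V5 has two (2 and 3).

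**Safeguards.** These are a symptom query after each dose and readiness of subject and staff (Section 4); saturation monitoring in the scanner and supplemental oxygen as indicated (Section 10); and heart-rate and SpO2 recovery before the next dose, withdrawal rules, and discontinuation of the trial after any serious adverse drug experience (Section 13).

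**The concern.** The dosing rule and the safety statement describe different exposures. One has no upper limit on count apart from supply; the other covers up to four doses. A supply limit is not a safety limit, and it can move if production improves.

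A site following the protocol can therefore give more doses in a session than the protocol's own safety statement covers. These patients have impaired gas exchange, and some may need supplemental oxygen. Section 10 itself names oxygen-free dosing as a risk. A reader of that section, such as an ethics committee, would see a description of one breath and not of the session that the procedures allow.

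**Working it through.** The plan gives no figure of its own to reproduce here. The check compares the permitted dose count with the cited count, and then looks at volume per dose.

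**Inputs from the documents**
- Cited maximum: 4 doses of 1 L (Section 3).
- Usual supply: 5 doses (Section 4).
- Xenon acquisitions per pass: 2, namely spectroscopy with calibration, and gas exchange imaging (Sections 4 and 9).
- Passes: 2 at V1, 1 at each of V3 to V5 (Section 9).
- Per-dose ceiling: 25% of TLC (Section 9).

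**Assumptions**
- One dose per xenon scan. Section 4 pairs each next dose with a scan but does not state this as a rule.
- The breath-hold 3D radial scan of the thoracic cavity uses no xenon.

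**Dose count**

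Doses in a session = acquisitions x passes + repeats (r).

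| Visit | Full list | Doses with r repeats | Exceeds the cited 4 when |
|---|---|---|---|
| V1 | 2 x 2 = 4 | 4 + r | r is 1 or more |
| V3, V4, V5 | 2 x 1 = 2 | 2 + r | r is 3 or more |

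At V1 the margin is 4 - 4 = 0. One repeat gives 4 + 1 = 5, which is above the cited count and still within usual supply.

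Two qualifications apply. Section 9 says that one or all of the listed data may be acquired, so four is the full V1 sequence and not a minimum. If the radial scan did use xenon, the V1 count would be 3 x 2 = 6, above four without any repeat.

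**Volume per dose (secondary)**

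0.25 x TLC = 1 L gives TLC = 4 L. The ceiling exceeds the cited 1 L only in subjects with TLC above 4 L. The documents give no TLC, so the values below are an assumed range.

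| Assumed TLC (L) | 3 | 4 | 5 | 6 | 7 |
|---|---|---|---|---|---|
| Ceiling per dose (L) | 0.75 | 1.00 | 1.25 | 1.50 | 1.75 |

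**Do the safeguards close the gap?** The recovery rules govern when the next dose may be given. The withdrawal and stopping rules end dosing once a subject has reacted. A subject who tolerates each dose meets none of them, so the number of doses in that subject remains open.

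**The case against.** The strongest reply is that nothing here contradicts anything else. Section 3 reports past experience and sets no limit; Section 4 is a deliberate design choice. The listed scans stay within four at every visit, and only optional repeats go beyond. The safeguards are real: subjects are questioned after every dose and monitored throughout scanning, and those who do not tolerate dosing are withdrawn. Section 4 adds that the per-dose limit is the one used in all current protocols under the same IND, and note 7 to the Schedule of Events refers to the imaging team's SOPs. Either source might support or cap the permitted exposure.

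Much of this stands. There is no formal contradiction, and the IND file and SOPs cannot be judged from these documents. What remains is that the protocol rests its safety case on a stated experience and then permits more than that experience without citing anything further. The usual supply of 5 doses does not answer this, because 5 is already more than 4.

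Two stronger readings are tempting and are not supported.

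- **Session volume far above the cited 4 L.** This needs TLC values that the documents do not give, and every dose at the ceiling. At an assumed TLC of 3 L, five ceiling doses total 5 x 0.75 = 3.75 L, below 4 L; at 6 L they total 5 x 1.5 = 7.5 L. Section 10 also frames the hazard per breath (alveolar concentration, and residual oxygen during the breath-hold), which a TLC-relative limit fits. It says effects wane within 1 to 2 minutes. Nothing in the documents treats summed liters as the relevant exposure.
- **More withdrawals from unlimited repeats.** No rate is given from which to estimate this, and Section 3 reports no withdrawals in the earlier studies.

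**Conclusion.** The point holds on dose count. The protocol permits an open number of xenon doses per session, the only multi-dose experience it cites is up to four 1 L doses, and the full V1 sequence uses all four. The excess begins at the first repeat at V1; at V3 to V5 it would take three. This rests on one dose per scan and on the radial scan using no xenon.

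Volume per dose is a secondary mismatch, confined to subjects with TLC above 4 L, whose number is unknown.

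A reader might infer that the procedure is unsafe or that the safeguards are absent. The documents show neither. They show a permitted exposure that the stated safety basis does not fully describe. It should be corrected because it bears on patient safety and can be settled largely in wording.

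**What to change.** Reconcile Sections 3, 4, 9 and 10 so that the number and volume of doses permitted per session match the exposure supported by the safety data relied on, and so that the risk section describes that exposure. If data under the IND already cover the permitted exposure, citing them would serve. How the match is made, and with what values, is for the sponsor and the IND holder. State at the same time whether each xenon scan uses one dose, so that the planned count at V1 can be read directly.

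The cost is mainly protocol wording, and consent wording if the described exposure changes. There is one real downside. If the reconciliation restricts repeats, a failed V1 acquisition might not be recoverable in the same session. That could lose a test-retest pair from the futility analysis in Section 12, which uses the first 10 patients. The return visit in Section 6 covers procedures cancelled for technical reasons, and a scan on another day does not replace a retest after a 5-minute rest. The sponsor should weigh this when settling the wording.
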